Unfortunately, there are disadvantages to the use of an anticholinesterase. Firstly, there is a "ceiling" effect, i.e. "once the acetylcholinesterase enzyme is maximally inhibited by an anticholinesterase agent and peak concentrations of acetylcholine are present, the administration of additional drug will not further increase acetylcholine levels or enhance recovery of neuromuscular blockade" (2, p. 842). Secondly, the use of an anticholinesterase with relatively mild residual blockade may lead to paradoxical muscle weakness. Thirdly, anticholinesterase agents have a multitude of adverse effects due to their muscarinic effects such as nausea, bradycardia, and bronchospasm. (2) Thus, an alternative method to antagonize the non-depolarizing NMBAs came to be a topic of research.

It was in this context that sugammadex was found to be a valuable addition to the anesthesiologist's armamentarium. It is a modified γ -cyclodextrin that encapsulates the aminosteroid NMBAs rocuronium and vecuronium. It was first discovered by the Organon Laboratories in Scotland and was then known as the agent Org 25969. The successful results of the first *in vivo* study was published in 2002 (3), where rocuronium was reversed in anesthetized monkeys, and the first phase I study was published in 2005 (4). It was approved by the United States Food and Drugs Administration (FDA) in 2015, with the following three dosing ranges, i.e. 2 mg/kg if the train-of-four (TOF) stimulation reaches the second twitch, 4 mg/kg if there is no twitch response to TOF stimulation but there are 1 to 2 post-tetanic counts (PTC), and 16 mg/kg after administration of 1.2 mg/kg of rocuronium (5).

Page 4 of 30 Version: 3 (10/14/2024)

In the clinical assessment of NMBA reversal, a TOF ratio¹ of 0.7 was historically seen as adequate, but this has been revised in the face of recent evidence that showed a TOF ratio of any less than 0.9 could result in "impaired pharyngeal function, airway obstruction, an increased risk of aspiration of gastric contents, an impaired hypoxic ventilatory control, and unpleasant symptoms of muscle weakness" (2, p. 836). Even if the TOF stimulation count is 4 but there is still detectable TOF fade, the TOF ratio will equate to 0.1-0.4 (6); this does not significantly change with a 5-second, 50-Hz tetanic stimulation (TOF ratio ~0.3) and is only slightly improved with double-burst stimulation (TOF ratio ~0.6-0.7) (2).

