These patients will be randomized using the Emory University REDCap (Research Electronic Data Capture) software to six groups: 2 mg/kg (the lowest dose approved by the FDA), 1 mg/kg, 0.5 mg/kg, 0.25 mg/kg, 0.125 mg/kg of sugammadex and placebo. Doses would be based on actual body weight. The time taken to reach a TOF ratio of 0.9 thereafter would be measured. If the patient fails to achieve this goal by 10 minutes, sugammadex would be given in 2 mg/kg increments until the patient reaches this threshold and can be safely extubated. The TOF ratio would be measured again at 30 minutes after arrival at the PACU to exclude delayed residual NMB with the plan to give further 2 mg/kg doses of sugammadex if detected.

The inclusion of a placebo group would allow us to examine if patients may recover spontaneously over that time without needing any sugammadex at all, and what parameters may predict that subset of patients. It will also improve the dose response modelling, in that randomization has been weighted so that patients who are least likely to need sugammadex (i.e. if they achieved a TOF count of 4 twitches without fade) are more likely to be in the placebo group or at the lowest dose of sugammadex that is being tested.

The time taken to a TOF ratio of 0.9 after the intervention drug has been given would be compared for statistically significant differences, controlling for the:

- TOF count (3 twitches, 4 twitches with fade, 4 twitches without fade), and
- TOF ratio (0 to < 0.9)

15 minutes after neostigmine has been given and prior to giving the intervention drug.

Quantitative neuromuscular monitoring will be carried out using electromyography, which measures the TOF ratio every 20 seconds. The TOF count (between 0 to 4) and the TOF ratio (0 to 1) would be measured and recorded at baseline and after administration of the study drug. If the TOF ratio remains < 0.9 after this, or if the patient exhibits any symptoms or signs of residual NMB blockade, a further 2 mg/kg dose of sugammadex would be given until the patient achieves a TOF ratio of 0.9.

Page 8 of 30 Version: 3 (10/14/2024)

7. Statistical Analysis Plan

Power Analysis

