Assuming assumptions are valid, an increasing exponential regression model with random intercept will be fitted with Time of Four Ratio versus Time, stratified by the natural log of the five dose levels (modeled below). This translates to a slow response initially followed by a more rapid response later. The random intercept will allow for different initial TOFR values.

Page 9 of 30 Version: 3 (10/14/2024)

$$TOFR = \frac{1}{B}e^{(A+time)/B} + TOFR_{initial} + C * \ln(dose)$$

"Success" will be defined as TOFR of ≥0.9 within 5 minutes for 95% of patients, following the model estimate, adjusting for the 95% confidence intervals of the estimates, based on initial TOF ratios, which may be grouped as needed. A secondary analysis will be conducted by TOFC to determine optimal dose at each TOFC level, and if TOFC correlates strongly with TOFR.

8. Data and/or Specimen Banking

N/A

9. Sharing of Results with Participants

N/A

10. Study Timelines

All subjects are anticipated to participate in the study from the start of their surgery to the time of their discharge from the PACU, which should be on the same day. It is expected that 1 year would be required to enroll all study subjects, and for the study to be completed by July 2023.

11. Inclusion and Exclusion Criteria

Individuals will be screened for eligibility at the anesthesia pre-admission clinic.

Inclusion criteria:

- Patients aged 18 years and above who will
- Undergo an elective surgery in the main operating room or outpatient surgery center at Grady Memorial Hospital,
- Receive general anesthesia (standardized to sevoflurane for maintenance),
- Receive rocuronium for NMB,
- Receive neostigmine for NMB reversal,
- Achieve a TOF count of at least 3 twitches but not a TOF ratio of 0.9 fifteen minutes after neostigmine has been given, and
- Able and willing to provide informed consent.

Exclusion criteria:

Page 10 of 30 Version: 3 (10/14/2024)

- Pregnancy and/or lactating,
- BMI ≥ 40,
- Severe renal impairment, i.e. chronic kidney disease stages IV and V as defined by GFR < 30 ml/min/1.73 m² (21),
- Severe hepatic impairment, i.e. Child-Pugh score C⁵ (22, 23),
- Pre-existing neuromuscular disease,
- Anticipated need for postoperative intubation, and/or
- Known hypersensitivity reactions to rocuronium, neostigmine and/or sugammadex.

12. Population

We will not be including the following special populations:

- Adults unable to consent
- Individuals under the age of 18 years
- Pregnant women

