- Did not require general anesthesia for surgery,
- Did not require NMB,
- Did not receive neostigmine for NMB reversal,
- Had a TOF count < 3 or a TOF ratio ≥ 0.9 fifteen minutes after neostigmine, or
- Remained intubated in the immediate postoperative period.

As the study intervention is a one-time dose of the study drug in the OR, no further action should be required if the patient decides to later withdraw from the study. The study will be terminated when the number of participants has reached the required threshold.

17. Risk to Participants

The most common risks of sugammadex as listed by the FDA (5) include:

- Nausea (23-26%)
- Vomiting (11-15%)
- Pain (36-52%)

Uncommon but serious risks of sugammadex include:

- Hypotension (4-13%)
- Tachycardia (2-5%)

Page 12 of 30 Version: 3 (10/14/2024)

- Bradycardia (1-5%)
- Anaphylaxis (0.3%)

Notably, all of these are known to be risks of general anesthesia as well as surgery and are routinely monitored for and treated in the PACU.

18. Potential Benefits to Participants

All study subjects will have any residual NMB reversed, which will prevent any postoperative complications such as respiratory compromise or weakness.

19. Compensation to Participants

N/A

20. Data Management and Confidentiality

Data to be collected include:

- Baseline demographics: MRN, date of birth, sex (male/female), race (white, black, American Indian or Alaska Native, Asian, Native Hawaiian or Other Pacific Islander, two or more races), ethnicity (Hispanic or Latino, not Hispanic or Latino), weight (kg)
- ii. Preoperative details: ASA status (I-IV)
- iii. Surgery details: date of surgery, diagnosis, surgery, start case time (hr: min), end case time (hr: min)
- iv. Anesthesia details: if succinylcholine was used (Y/N), total amount of rocuronium given (mg), the last dose of rocuronium that was given (mg), the time that the last dose of rocuronium was given (hr:min), neostigmine dose (mg), the time that neostigmine was given (hr: min), the time that the study drug was given (hr: min).
- v. TOF ratio (0-1)
 - Before any paralytic is given at the start of the case
 - Before neostigmine is given at the end of the case
 - Before the study drug is given
 - 30 minutes after PACU arrival
- vi. TOF count (0-4 ± fade)
 - Before neostigmine is given at the end of the case
 - Before the study drug is given
- vii. The time taken to achieve a TOF ratio of 0.9 (seconds).

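### Neostigmine dose and pre-neostigmine block depth are recorded but used in no planned analysis, so the rescue dose is estimated over an undefined reversal background

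*Combined protocol and SAP*

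**What the plan says.** All references are to the combined protocol and SAP.

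- **Entry (section 11).** Patients must "Receive neostigmine for NMB reversal". The only condition on the result is that they "Achieve a TOF count of at least 3 twitches but not a TOF ratio of 0.9 fifteen minutes after neostigmine has been given". No section gives a neostigmine dose for participants or a TOF count or ratio at which it is to be given. The same list does standardise the maintenance anaesthetic, to sevoflurane.
- **Comparison (section 6).** Time to a TOF ratio of 0.9 is compared controlling for TOF count in three classes and for TOF ratio, both taken "15 minutes after neostigmine has been given and prior to giving the intervention drug".
- **Randomisation (section 7, Methodology and Table 1).** Stratified by initial TOF count only, with six patients per dose in total.
- **Model (section 7, Statistical Methodology).** TOF ratio is modelled on time, initial TOF ratio (random intercept) and ln(dose). Success is a ratio of at least 0.9 within 5 minutes for 95% of patients, read from the model by initial ratio.
- **Data (section 20).** The form records "neostigmine dose (mg), the time that neostigmine was given (hr: min"), weight, TOF ratio and count before neostigmine, and the total and last rocuronium dose with the time of the last one. No analysis names any of these as a covariate.

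**The concern.** Section 3 describes two drugs that act at different places. Neostigmine raises acetylcholine at the junction and leaves the rocuronium where it is. Sugammadex "encapsulates the aminosteroid NMBAs rocuronium and vecuronium". A TOF ratio measured after neostigmine therefore depends both on how much rocuronium remains and on how strongly its effect is being opposed. Only the first of these is what sugammadex binds.

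Take two patients with a ratio of 0.6 at 15 minutes. One received more neostigmine from a deeper block, the other less from a shallower block. The section 6 adjustment treats them as alike if their counts match, and the section 7 equation gives them the same curve at the same dose. They may nevertheless need different amounts of sugammadex.

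This bears most directly on the success rule. A 95%-of-patients target depends on the tail of between-patient variation, and the only patient-level term in the model is an intercept for the starting ratio. The reported dose would carry no statement of the neostigmine exposure over which it was found.

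**Working it through.** **1. Can the 15-minute ratio stand in for the background?** Section 3 reports residual block 15 minutes after neostigmine in 39% of patients reversed from moderate block and 99.1% of those reversed from deep block. Depth before neostigmine thus strongly affects who fails. Both kinds of failure can enter this trial if the count has reached 3 by 15 minutes. These figures do not show how much depth matters once the 15-minute ratio is known, and nothing else in the documents does.

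**2. How wide could the background be?** The adult per-kg neostigmine doses cited in section 3 are 0.034, 0.05 and 0.07 mg/kg, so 0.07/0.034 = 2.06-fold. They come from other studies in other settings. They illustrate a spread and do not describe practice at this site.

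**3. The plan's own sample size.** One-way ANOVA, noncentrality λ = N·f², df = (k−1, N−k), f = 0.765, α = 0.05.
- Four groups (as in the source trial), N = 24: λ = 24 × 0.5852 = 14.05, df (3, 20), power 0.824. This reproduces N = 24.
- Six groups (as randomised), N = 36: λ = 36 × 0.5852 = 21.07, df (5, 30), power 0.920. This is the baseline below. The choice of four or six groups for N = 24 is a separate matter.

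**4. Effect of added variance.** The documents give no variance for neostigmine dose, depth or rocuronium load, so the share is assumed. If the open background makes up a share s of within-arm variance, over and above the variance behind f, then f becomes 0.765·√(1−s). Six groups, N = 36, no adjustment:

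| s (assumed) | f | Power |
|---|---|---|
| 0 | 0.765 | 0.920 |
| 10% | 0.726 | 0.886 |
| 25% | 0.663 | 0.812 |
| 40% | 0.593 | 0.705 |
| 50% | 0.541 | 0.613 |

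This concerns the omnibus test used for sizing, not the exponential model.

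**5. Chance imbalance.** For a baseline factor unrelated to the strata, the difference between two arm means of six has SD √(1/6 + 1/6) = 0.577 of the factor's SD. It exceeds 0.5 SD with probability 2·(1 − Φ(0.5/0.577)) = 0.386. If neostigmine fell into two levels used equally often (an assumption), two arms of six would differ by at least 2 patients with probability 1 − (792 + 924 + 792)/4096 = 0.388. They would differ by at least 3 with probability 0.388 − 990/4096 = 0.146.

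**6. Cost of adjusting.** Two covariates that explain nothing change the df to (5, 28), and power goes from 0.920 to 0.916.

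**The case against.** The strongest reply is that reversal is background care in this trial. Section 6 identifies patients who have had neostigmine and are still not recovered, and the question is what to give from that state. On that reading the 15-minute count and ratio are the right conditioning variables.

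Much of this stands:

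- A reader might infer that patients given little neostigmine fall outside the objective. Section 2 speaks only of inadequate reversal with neostigmine and does not say a full dose, so they are within it.
- A reader might infer that more neostigmine always hides more rocuronium. Section 3 describes a ceiling beyond which further drug adds nothing, and does not say where in the cited range it lies. Over part of that range there may be no difference.
- The entry filter narrows the spread: counts of 0 to 2 at 15 minutes get no study drug, and assessment is fixed at 15 minutes.
- The probabilities in step 5 hold for any comparable factor in two arms of six. They show how easily imbalance arises and do not measure harm to the dose estimate.
- Section 6 plans to look at parameters that predict recovery without sugammadex. They are not listed, however, and the stated purpose is the placebo group, so this does not cover the dose comparison.

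What the reply does not answer is that the background is recorded, is known before randomisation, and is left out of both the adjustment and the statement of the conclusion. If open dosing is deliberately pragmatic, the documents do not say so.

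**Conclusion.** The gap is confirmed by the text and should be closed, but its size is unknown. It lies in analysis and reporting, not in data capture.

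Randomisation within TOF-count strata means the background cannot systematically favour one dose within a stratum. The pooled comparison keeps that protection as long as it controls for TOF count, as section 6 plans. The harm is of three kinds: variance left unexplained, chance imbalance with six per arm, and a success claim with no stated neostigmine exposure.

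It might be inferred that the selected dose will be too low for patients who failed a larger neostigmine dose. The documents do not support that: they give neither the site's neostigmine practice nor any effect of it at a given 15-minute ratio. The power range of 0.89 to 0.61 rests entirely on the assumed 10% to 50% shares. The near-zero cost of adjustment rests on the plan's own f, α and N.

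**What to change.** 1. In section 6 and the section 7 model, add neostigmine mg/kg (recorded dose divided by recorded weight) as a prespecified pre-randomisation covariate.
2. Add block depth before neostigmine as a second covariate or in a sensitivity analysis. Code it from TOF count, with TOF ratio used where four twitches are present. The ratio alone will not do: it is the fourth twitch over the first (footnote 1, section 3), so it is zero or undefined below four twitches and cannot grade deeper block. A single ordered score (count plus ratio) keeps this to one term, at the price of assuming linearity.
3. As a further sensitivity analysis, use the amount of the last rocuronium dose and the time since it was given.
4. State the success conclusion for the range of neostigmine mg/kg actually given, and report that range by arm.

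The cost is SAP wording and one or two degrees of freedom at N = 36, with no new data. It should be settled before results by dose are seen. No change is proposed to neostigmine dosing or to the block depth at which it is given. The documents contain no contradiction on either, and the choice belongs to the investigators.

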An *a priori* power analysis was conducted using G*Power 3.1.9.4 (20). We used an ANOVA F-Test for one-way omnibus difference between groups, alpha threshold of 0.05 for rejecting the null hypothesis, statistical power of 0.80 and a "very large" effect size of 0.765 was calculated based on results from a 2013 randomized controlled trial that examined time from TOF count = 4 to TOF ratio 1.0 comparing neostigmine to three different doses of sugammadex: 0.5, 1.0, and 2.0 mg/kg (15). This gave a required sample size of N=24. This number was increased to N=36 to account for patients with poor modeling from a high starting TOFR (resulting in few data points for that patient) or incomplete recovery within the maximum ten minutes allotted. An anticipated 70% of those enrolled will become ineligible because of an initial TOFR of 90% or greater, thus not requiring any medications, so up to 120 patients may need to be recruited and screened, but only 36 will receive any treatment.

Methodology

Randomization will occur with permuted block randomization, divided into 18 groups, to ensure proportional allocation of participants in each group over time. Dose randomization will be assigned after stratifying by initial TOFC, with a set number of patients recruited for each group, as seen the table below. This ensures that patients who likely need a lower dose are more likely to receive it. Randomization will not occur until participation is assured, i.e., their TOFR is <0.90.

Table 1: Randomization plan for patients (n=36)

| Sugammadex Dose (mg/kg) → | | 0.00 | 0.125 | 0.25 | 0.50 | 1.00 | 2.00 | | | |
|---------------------------|-----------------|------|--|----------|------------|---------|---------|------|-------|----|
| Initial TOFR | Initial TOFC | Fade | placebo | | | | | | Total | |
| ≥ 0.9 | NA | NA | No treatment; track for adverse events | | | 0 | | | | |
| | | 4 | No | 3 pt | 3 pt | 2 pt | 2 pt | 1 pt | 1 pt | 12 |
| < 0.9 | 4 | Yes | 2 pt | 2 pt | 2 pt | 2 pt | 2 pt | 2 pt | 12 | |
| | 3 | NA | 1 pt | 1 pt | 2 pt | 2 pt | 3 pt | 3 pt | 12 | |
| < 0.9 | 0-2 | NA | No t | treatmen | t; track f | or adve | se even | ts | 0 | |
| Total # of Patients (pt) | | | 6 | 6 | 6 | 6 | 6 | 6 | 36 | |

Statistical Methodology

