- Prisoners
- Cognitively impaired or Individuals with Impaired Decision-Making Capacity
- Individuals who are not able to clearly understand English

Racial and ethnic classification of subjects would be collected from their electronic medical record (which is based on self-identification) for descriptive statistics. Race would comprise the following six categories: white, black or African American, American Indian or Alaska Native, Asian, Native Hawaiian or Other Pacific Islander, and two or more races. Ethnicity would be either Hispanic/Latino or not Hispanic/Latino. This information will not be used as a variable to explain differences between participants, but will be presented in Table 1 as part of the study's demographic data, which may help in assessing if the study could be generalized to other patient populations in turn.

The number of individuals who are not able to clearly understand English constitute a minority of the patient population at Grady Memorial Hospital.

13. Vulnerable Populations

N/A

14. Local Number of Participants

Up to 120 patients may need to be enrolled and screened, but only 36 will receive any treatment. We anticipate a similar percentage of participants according to sex, but the majority

Page 11 of 30 Version: 3 (10/14/2024)

⁵ Child-Pugh classification includes bilirubin, INR, albumin, ascites and encephalopathy. A total score of 5-6 is class A, 7-9 is class B and 10-15 is class C.

would likely be either white or black due to general patient demographics in Grady Memorial Hospital.

15. Recruitment Methods

All patients presenting to the anesthesia pre-admission clinic as well as inpatients scheduled for the operating room the next day would be screened via electronic medical record on a day-to-day basis to determine if they are eligible to participate in the study. Eligibility screening would be determined based on their most recent surgical notes (i.e. whether the patient would likely undergo general anesthesia as well as NMB).

Patients who are eligible would then be contacted and introduced to the study by a study team member for potential recruitment, at a minimum the day before the date of surgery in order to allow enough time for the patient to consider the risks and benefits of participation.

16. Withdrawal of Participants

Patients may be withdrawn from the research study without their consent if they are found to not meet the study's inclusion criteria, e.g.

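### Section 16 lets the team withdraw a randomized, dosed patient for remaining intubated, and no rule keeps that patient in the analysis

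*Combined protocol and SAP*

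**What the plan says.** Section 16 (Withdrawal of Participants) opens with: "Patients may be withdrawn from the research study without their consent if they are found to not meet the study's inclusion criteria". Five examples follow. Four are no general anesthesia, no neuromuscular blockade, no neostigmine, and a non-qualifying TOF result: "Had a TOF count < 3 or a TOF ratio ≥ 0.9 fifteen minutes after neostigmine, or". The fifth is "Remained intubated in the immediate postoperative period".

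The nearest item in Section 11 is an exclusion criterion judged in advance: "Anticipated need for postoperative intubation, and/or".

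Section 7 (Methodology) fixes the time of allocation: "Randomization will not occur until participation is assured, i.e., their TOFR is <0.90". Section 6 then describes study drug, up to 10 minutes of measurement, and rescue: "If the patient fails to achieve this goal by 10 minutes, sugammadex would be given in 2 mg/kg increments until the patient reaches" the target, with the end point given as "until the patient reaches this threshold and can be safely extubated".

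**The concern.** A ground for withdrawal that can come into being after treatment is not an eligibility check. Failure to extubate can follow from inadequate reversal, which is what the trial measures. If such a patient is withdrawn and the data are then left out, the exclusion is related to outcome, and the randomized comparison no longer covers everyone who was randomized and dosed.

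The analyses exposed are the time to a TOF ratio of 0.9, the percentages reaching it by 1, 2, 5 and 10 minutes, and the dose judged sufficient under the Section 7 success rule (0.9 within 5 minutes for 95% of patients, from the model). Each arm holds six patients, so a single exclusion is visible in the result.

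**Working it through.** **Step 1. When each Section 16 ground becomes known.**

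| Ground | Known by | Relative to randomization |
|---|---|---|
| No general anesthesia | Surgery | Before |
| No neuromuscular blockade | Surgery | Before |
| No neostigmine | Reversal | Before |
| TOF count or ratio outside range | 15 minutes after neostigmine | Before |
| Still intubated postoperatively | When extubation is due | For a dosed patient, after study drug and any rescue |

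Only the fifth can apply to a patient who qualified, was randomized and was dosed.

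**Step 2. Section 16 against Section 11.** Section 16 presents the fifth ground as a failed inclusion criterion. Section 11 lists no such criterion. It excludes an anticipated need for intubation, which is a judgement made beforehand. The two sections do not agree.

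**Step 3. Who would meet the ground.** Under Section 6, a patient not at 0.9 by 10 minutes receives rescue whatever the arm, until extubation is safe. An ordinary failure of the assigned treatment should therefore end up extubated and fall outside the ground. Those left are patients intubated despite rescue or for reasons other than blockade. The postoperative period has no clock time, so a wider reading that takes in slow recoverers is not ruled out.

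**Step 4. What protects the data of a withdrawn patient.** Section 7 defines no intention-to-treat or other analysis set. Section 16 does not say whether data up to withdrawal are used, or whether the patient is replaced. It ends the study when the required number of participants is reached, without saying whether withdrawn patients count. Section 20 requires records to be stored for at least 6 years, which concerns storage and not analysis. Its rule on partial participation concerns the patient's choice, not withdrawal by the team.

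**Step 5. Effect of one exclusion on an arm.** Table 1 gives 36/6 = 6 patients per arm. With s responders, removing one failure changes s/6 to s/5, a rise of s/30. Removing one responder changes s/6 to (s − 1)/5, a fall of (6 − s)/30.

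| s | All six kept | One failure removed | One responder removed |
|---|---|---|---|
| 5 | 5/6 = 83% | 5/5 = 100% | 4/5 = 80% |
| 4 | 4/6 = 67% | 4/5 = 80% | 3/5 = 60% |
| 3 | 3/6 = 50% | 3/5 = 60% | 2/5 = 40% |

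In Table 1 the TOF count 3 row is 1, 1, 2, 2, 3, 3 from placebo to 2 mg/kg. One withdrawal empties the placebo or the 0.125 mg/kg cell, and Section 7 plans a secondary analysis by TOF count.

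**Step 6. Effect on power.** Section 7 uses a one-way ANOVA F-test with f = 0.765, alpha 0.05 and power 0.80. The noncentrality is N × f². With four groups (as in the cited trial) and N = 24, it is 24 × 0.765² = 14.05 and power is 82.4%. This reproduces the plan's 24 as the smallest balanced size. With this trial's six groups and N = 36, it is 36 × 0.765² = 21.07 and power is 92.0%. Assuming group means equally spaced by dose rank, power becomes:
- one placebo patient removed (N = 35): 89.8%
- one placebo and one lowest-dose patient removed (N = 34): 88.7%
- two of each removed (N = 32): 83.9%
- three of each removed (N = 30): 76.8%

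Losing one or two patients costs little power. The issue is which patients are lost.

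**The case against.** A reader might infer that the clause strips treatment failures out of the placebo and low-dose arms and so pushes the result towards the trial's hypothesis. The documents do not support that.

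- The Section 6 rescue rule applies to all arms and leads ordinary failures to extubation. Concentration in the low arms is not shown.
- For such failures the 1, 2, 5 and 10 minute outcomes have been observed before postoperative intubation status is known. Nothing says that withdrawal deletes them.
- The direction is not fixed. The Section 7 model uses the five non-zero doses through ln(dose), so losing placebo patients would not move the dose term as written. In the comparison with placebo, losing placebo failures would shrink the contrast. A patient intubated for other reasons may already have reached 0.9.
- The trial is double-blind, which limits selection by arm, though not by outcome.

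A reader might also infer that a serious safety event would disappear. Section 21 collects serious and any other adverse events to PACU discharge, for participants and screen failures alike. Prolonged intubation is, however, neither a named safety outcome in Section 4 nor a listed data item in Section 20.

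Finally, the item could be meant for a patient unexpectedly left intubated who never reaches study drug. The screening character of the other four grounds favours that reading, but the words do not confine the item to it. Section 7 also raises N from 24 to 36 partly for incomplete recovery within ten minutes. That can be read as expecting such patients among the 36, or as expecting them to be lost to the model, so it settles nothing.

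What stands of the objection is that the effect may be rare and its direction uncertain. It does not remove the permission to withdraw.

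**Conclusion.** The point holds in a limited form. Section 16 states a withdrawal ground that is not a Section 11 criterion and that can apply after randomization and study drug. No analysis-set rule prevents the resulting exclusion. This is a stated rule and not only an omission, so it calls for correction.

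Its frequency and its distribution by arm are unknown. The percentages in the working show what one exclusion would do. They do not predict that it will happen. They are also observed proportions, whereas the success rule works through the model. With six patients per arm, one lost failure raises an arm's observed rate by 10 to 17 percentage points when three to five of the six respond. The conclusion assumes that a site could apply the ground to a dosed patient, which the text allows, and that a withdrawn patient could then be left out of the analysis, which no text forbids.

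**What to change.** 1. **Sections 11 and 16:** reconcile them so that withdrawal for ineligibility is limited to facts known before randomization.
2. **Section 7:** state that all randomized patients who received study drug are analysed in their assigned group with their data kept. State that a patient not at a TOF ratio of 0.9 before rescue counts as not having reached it in the percentage outcomes and is censored at rescue for the time outcome.
3. **Sections 20 and 21:** record prolonged intubation after study drug among the adverse events already collected.

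The cost is a few sentences and one recorded item. No extra patients or procedures are needed, because the TOF ratio is already measured every 20 seconds. The change should be made before results are seen, since a choice of analysis set made afterwards could not be shown to be independent of outcome.
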